effect. Shown in Figure 1, the proposed sample should be adequate (power=.80) to detect a moderate small effect of $f^2=.25$. Also shown in Figure 1, although larger samples would of course improve power to detect very small effects, the proposed sample of 80 evidences notable gains in power over a sample of 60. Given criticisms about the clinical value of very small effects, we are most interested in effects sizes that fall in the moderate range. Accordingly, the current sample should be well powered to detect effects that are clinically meaningful. Similar treatment studies of MBSR and MBCT with veterans and civilians support medium to large effect sizes for reduction in PTSD and depression symptoms ($d=0.59-0.99$).^[35, 42, 45, 46] Extrapolating from the effects indicated in these investigations, we should be well powered to detect significant effects across aims.

Data and Safety Monitoring Plan

The PI and study personnel have completed and passed the Human Subjects Protection Education Program provided by Emory University. Certification letters will be provided upon request. The present study is an intervention study and therefore we will complete a data safety monitoring plan to ensure oversight and monitoring of the study to ensure the safety of participants and the validity and integrity of the data. The PI will monitor safety issues throughout the study. Specifically, study progress and safety will be reviewed weekly (and more frequently if needed). The PI will work closely with [name] to monitor for potential adverse reactions of subjects to mindfulness exercises and if significant exacerbation of symptoms or safety concerns emerge, the subject will be offered immediate psychological services through the Grady Health System and NIA project. Progress reports, including subject recruitment, retention/attrition, and adverse events (AE) will be provided to an Independent Monitor (IM) semi-annually. The IM for this study will be the Data Safety Monitoring Board in the Department of Psychiatry and Behavioral Sciences. An Annual Report will be compiled and will include a list and summary of AEs. In addition, the Annual Report will address (1) whether AE rates are consistent with pre-study assumptions; (2) reason for dropouts from the study; (3) whether all participants met entry criteria; (4) whether continuation of the study is justified on the basis that additional data are needed to accomplish the stated aims of the study; and (5) conditions whereby the study might be terminated prematurely. The Annual Report will be sent to the IM and will be forwarded to the IRB.

Confidentiality

Confidentiality will be protected throughout the study and following completion of the study. This will be done in a number of ways. First, all participants will be assigned a subject ID and all data gathered and session notes will only contain de-identified information and their subject ID. Also, participants will be informed of the confidential nature of the study and informed of the limitations of confidentiality. Also, all participant information will be kept in a locked desk drawer in a locked office or stored on a password protected and secured electronic network.

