There is significant public health burden of chronic trauma exposure in low income, predominantly ethnic minority, urban communities, which is reflected in the extraordinarily high levels of trauma-related psychiatric disorders, particularly posttraumatic stress disorder (PTSD) and major depressive disorder (MDD). Despite this, limited access to behavioral health treatment and significant barriers to treatment engagement and success remain^[1] and integrating mind-body approaches in medical settings could be a critical next step in treating chronically traumatized individuals in these urban settings. This study will utilize a randomized controlled trial design along with a multi-method assessment approach to ascertain the feasibility, acceptability, and preliminary mechanisms of action and outcomes of mindfulness-based cognitive therapy versus wait-list control in 80 African Americans with chronic trauma exposure and comorbid PTSD and MDD symptoms. Subjects will be recruited from primary care waiting rooms at Grady Memorial Hospital. Individuals must screen positive for depression and PTSD in order to be eligible for the study through the Patient Health Questionnaire-9 and Primary Care PTSD Screen. Once enrolled, subjects will be randomized to an 8 session (90 minutes each) group intervention or wait-list control. We will examine retention and follow-up rates, subjects' report of acceptability and interest in the intervention, and examine barriers to treatment engagement through self-report measures and exit interviews. We will also investigate preliminary mechanisms of action and outcomes of the mindfulness intervention in targeting emotion regulation and autonomic processes by measuring self-report of emotion dysregulation using the Difficulties in Emotion Regulation Scale and autonomic arousal to trauma cues using Esense technology to assess skin conductance during administration of Standardized Trauma Interview. Latent growth modeling will assess relative changes in emotion dysregulation and autonomic function over time through intervention and 1 month follow-up.

Introduction and Background

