Specific Aim 1: Evaluate feasibility and acceptability of mindfulness intervention in a high-risk, underserved population. *Aim 1a: Examine retention and follow-up rates in the intervention and control groups.* Completion of assessments and intervention session attendance will be tracked. *Aim 1b: Examine subjects' report of acceptability of and interest in the intervention.* Satisfaction with intervention will be assessed with a self-report measure and through an exit interview post-intervention. Descriptive statistics and frequency distributions will be evaluated. *Aim 1c: Examine barriers to treatment engagement in the intervention.* Barriers to treatment will be assessed with a self-report measure and through descriptions provided by subjects post-intervention. Descriptive statistics and frequency distributions will be evaluated.

Specific Aim 2: Investigate preliminary mechanisms of action and outcomes of mindfulness intervention in targeting emotion regulation and autonomic processes. *Aim 2a: Evaluate if intervention results in greater reductions in ED than wait-list control.* Self-report ED (emotional awareness, acceptance, strategy use, behavioral control) data will be collected at four time-points (pre-intervention, half-way through intervention, post-intervention, 1m follow-up). *Aim 2b: Evaluate if intervention results in greater normalization of autonomic function than wait-list control.* Autonomic arousal to trauma cues (using skin conductance; pre- and post-intervention, 3 month follow-up) will be measured. Latent growth modeling (LGM) will assess relative changes in ED and autonomic function through intervention and follow-up.

Study design and methods

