Procedure: Initial screening for eligibility will occur in the medical clinics of Grady Memorial Hospital or through phone-based screening through a parent project, the Grady Trauma Project (IRB00078593). After initial screening through the Grady Trauma Project to determine eligibility for the study associated with this study and appropriate informed consent procedures, subjects will participate in a pre-intervention assessment. These may be in person or virtually depending on safety-related challenges due to the COVID-19 pandemic. Virtual assessments will either occur via phone or Zoom (HIPAA-compliant platform). Following the pre-intervention assessment, they will be randomly assigned using a random number generator to either the MBCT intervention or wait-list control group condition. We will use block stratified randomization (in blocks of 20) to ensure variability in PTSD and MDD diagnosis in the two groups. We will also use allocation concealment by placing the treatment allocation information in opaque envelopes so the study staff that are enrolling subjects do not know in advance which treatment condition will be assigned next. I will generate the allocation sequence and will not be in charge of recruiting subjects. I will also not be blind to assignment and will not collect dependent variables. In the case of virtual assignment to condition, 2 independent staff members not engaged in active recruitment or assessment will have the allocation sequence and will provide it to the staff member doing the pre-assessment following the completion of the interview. The

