staff members who will conduct the CAPS and MINI (to assess other Axis I disorders) will be blind to group assignment. The time requirement for the MBCT intervention group will be eight 90-minute sessions. Groups will be offered virtually. Subjects will be compensated \$10 for their time at each intervention session. Upon the completion of the 8 sessions (MBCT group) or 8 weeks after the pre-intervention assessment (assessment-only wait-list group), a post-intervention assessment will be conducted. Again, this may occur in person or virtually depending on COVID-19 conditions. One month later, a follow-up assessment will be conducted by phone or Zoom. The time requirement for the pre and post assessment will be ~3 hours and subjects will be compensated \$60 for these assessments. The follow up assessment will take approximately one hour and subjects will be compensated \$20 for that assessment.

Measures	Screen	Pre	Intervention (8 weeks)								Post	FU
			1	2	3	4	5*	6	7	8		
Traumatic Events Inventory	X											
Alcohol Use Disorders Identification Test	X											
Drug Abuse Screening Test	X											
Primary Care PTSD Screen	X										X	X
Patient Health Questionnaire-9	X										X	X
PTSD Checklist for DSM-5	X										X	X
Beck Depression Inventory, II	X										X	X
Standardized Trauma Interview (+ SC)		X									X	X
Difficulties in Emotion Regulation Scale		X		X	X		X		X		X	X
Clinician Administered PTSD Scale	X										X	
MINI International Neuropsychiatric Interview	X										X	
Five Facet Mindfulness Questionnaire	X										X	X
Self Compassion Scale, Short Form	X										X	X
PANAS	X										X	X
Client Satisfaction Questionnaire											X	
Perceived Barriers to Psychological Treatments											X	
Post-group Follow-up Questionnaire**											X	

*Assessment-only subjects will also fill out measures for intervention week 5.

**For group intervention participants only

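### Aim 2b skin conductance: the documents conflict on when and how the follow-up is done, and no analysis is written for the case where only pre and post exist

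*Combined protocol and SAP*

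**What the plan says.** **Timing.** Objectives, Aim 2b: "Autonomic arousal to trauma cues (using skin conductance; pre- and post-intervention, 3 month follow-up) will be measured". Objectives, Aim 2a, on emotion dysregulation: "data will be collected at four time-points (pre-intervention, half-way through intervention, post-intervention, 1m follow-up". The opening summary gives both outcomes the same horizon: "Latent growth modeling will assess relative changes in emotion dysregulation and autonomic function over time through intervention and 1 month follow-up". Study design and methods, Procedure, has a single follow-up: "One month later, a follow-up assessment will be conducted by phone or Zoom". The measures table has one follow-up column.

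**Mode.** The Procedure makes that follow-up remote. Of the pre-intervention assessment it says "These may be in person or virtually depending on safety-related challenges due to the COVID-19 pandemic", and of the post-intervention assessment "Again, this may occur in person or virtually depending on COVID-19 conditions". The section Physiological Response to Trauma records skin conductance with electrodes on the hands. It does so only when attending the laboratory is judged safe, and otherwise omits it. Against this, the table row "Standardized Trauma Interview (+ SC)" is marked at Pre, Post and FU, and the Setting paragraph places all three assessments on site.

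**Analysis.** Statistical analysis, Aim 2b, specifies a latent growth model with arm acting on the slope, and predicts lower arousal in the intervention arm both after the intervention and at follow-up. The Overall analytic approach has a general statement on missing data (frequentist or Bayesian estimation, multiple imputation). No version of the Aim 2b model is given for two waves.

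**The concern.** A reader cannot tell whether skin conductance has two or three planned waves, or when the third falls. If the Procedure and the physiology section are both followed as written, no participant has a follow-up value. Part of the stated hypothesis then cannot be examined, and the only model named for Aim 2b needs a constraint that the plan does not give. The analyst would choose that constraint after the data are in hand, for the trial's only physiological outcome.

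**Working it through.** The plan gives no figure for this point that could be reproduced. The check has three parts.

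**1. Where the last wave falls.** Inputs: post assessment at 8 weeks (Procedure; stated as 8 weeks after the pre-intervention assessment for the wait-list arm) and one month = 365.25/12/7 = 4.348 weeks.

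- One month after post: 8 + 4.348 = 12.3 weeks from baseline (12.348/4.348 = 2.8 months).
- Three months from baseline: 3 × 4.348 = 13.0 weeks.
- Three months after post: 8 + 13.045 = 21.0 weeks.

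The first two nearly agree; the third does not. To see whether this matters for a slope, assume that an effect of 1 unit is complete at post and holds to follow-up. With times 0, 8 and t, and values 0, 1 and 1, the least-squares slope is (mean time) / (sum of squared deviations of time):

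- t = 12.348: 6.783/78.46 = 0.086 per week
- t = 13.045: 7.015/86.54 = 0.081 per week
- t = 21.045: 9.682/225.68 = 0.043 per week

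This is an illustration under that assumption, not a forecast for the trial.

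**2. Whether a third wave exists.** Follow-up by phone or Zoom (Procedure) together with laboratory-only recording (Physiological Response to Trauma) means no skin conductance at follow-up. The table mark, the Setting paragraph and the Aim 2b hypothesis mean that there is. No section says which prevails. Because pre and post may also be virtual, two waves is the maximum under the Procedure text.

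**3. What two waves identify.** The Aim 2b text does not spell out the variance structure. Assume the usual linear growth model: random intercept (variance ψI), random slope (ψS), their covariance (ψIS) and residual variance θ, with time score 0 at pre and λ at post. With arm as predictor, the moments are T means + T arm regressions + T(T+1)/2 variances and covariances.

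- T = 2: 2 + 2 + 3 = 7 moments. The parameters are 2 growth means, 3 growth (co)variances, 1 or 2 residual variances and 1 or 2 arm effects, which makes 7 to 9.
- Arm on slope only: 7 or 8 parameters, Jacobian rank 6. Arm on intercept and slope: 8 or 9 parameters, rank 7. Every version is rank-deficient.
- The reason can be seen by hand. Var(pre) = ψI + θ1, Cov = ψI + λψIS and Var(post) = ψI + 2λψIS + λ²ψS + θ2 are three equations in four unknowns (equal residuals) or five (separate residuals).
- The arm effects enter only the arm regressions, which are γI at pre and γI + λγS at post. The arm-on-slope effect is therefore identified in all four versions.
- Fixing the residual variance restores full rank: 6 parameters with rank 6, or 7 with rank 7.
- T = 3: 3 + 3 + 6 = 12 moments against 7 to 10 parameters, full rank. The planned model works if the third wave exists.

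The two constrained two-wave models were compared with familiar estimators in 200 simulated data sets (40 per arm; residual variance fixed at 0, 0.1 and 0.2). Arm on slope only reproduced the baseline-adjusted (ANCOVA) estimate to within 2.5e-7. Arm on both reproduced the difference in change scores to within 2.1e-7.

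**The case against.** **The 3 months is probably a slip.** Every other statement of follow-up timing says one month, the table has one follow-up column, and three months from baseline is within a week of the one-month visit. This is a likely explanation, and a 21-week visit should not be inferred, since the procedures contain none. But Aim 2b does not say that it counts from baseline, and the adjacent Aim 2a text labels the follow-up as one month. The wording still needs correcting.

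**Skin conductance could be recorded at a separate laboratory attendance.** The physiology section can be read as allowing an in-person visit for that component alone. The Procedure provides none at follow-up. The Setting paragraph cannot settle it: it also puts group sessions in clinic rooms, whereas the intervention text holds them by Zoom.

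**Missing data are already covered.** The general provision can handle sporadic gaps, including a participant with only one of pre and post. It cannot supply a wave that nobody has.

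**Stronger readings that the documents do not support:**

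- That Aim 2b becomes untestable. It does not, because the arm effect on change is identified and a routine constraint suffices.
- That choosing between ANCOVA and change scores alters what is estimated. Randomization follows the pre-intervention assessment, so with complete data both target the same effect. They differ in precision and in how they treat chance baseline imbalance.
- That the visit length is part of the conflict ("The follow up assessment will take approximately one hour"). The table omits the two long diagnostic interviews at follow-up, so a shorter visit is expected. Only the mode conflicts.
- That the power statement fails for Aim 2b. The documents give no figure for how many participants will have skin conductance, so nothing can be calculated.
- That the growth model should be replaced in any case. With three waves it is identified and can stand.

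**Conclusion.** The concern holds in a limited form. The documents contradict each other on the timing and mode of the skin conductance follow-up, and nothing in them resolves it. Under the Procedure text there are at most two waves, the follow-up part of the Aim 2b hypothesis has no data, and the usual growth model is not identified in its variance components (7 moments, 7 to 9 parameters, rank 6 or 7). The pre-to-post comparison between arms survives.

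This rests on two assumptions: that the remote follow-up and the laboratory-only rule both apply as written, and that the growth model has random intercept, random slope and free residual variance, which the plan does not state. Aim 2 is presented as a preliminary look at mechanisms, so the consequence is modest. It is still worth settling before analysis.

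**What to change.** Reconcile the opening summary, Objectives (Aim 2b), Procedure text, measures table, Physiological Response to Trauma, Setting and Statistical analysis (Aim 2b) on three things: when the follow-up falls, how it is conducted, and whether skin conductance is collected there. Then write one of two branches.

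- **No skin conductance at follow-up.** Prespecify for Aim 2b a regression of post-intervention skin conductance response on arm and pre-intervention response, plus the PTSD and MDD stratification factors used in randomization (which the Procedure should define). Limit the hypothesis to post-intervention. Apart from the stratification terms, on complete data this gives the same estimate as the planned arm-on-slope model with its residual variance fixed.
- **Skin conductance collected in person at follow-up.** Keep the planned growth model and code time in actual weeks from baseline, as the Aim 2a analysis already does for emotion dysregulation.

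The first branch costs only wording, and its downside is that the trial makes no follow-up claim for skin conductance. The second requires the Procedure to provide for laboratory attendance at follow-up, which is an operational change.

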that will be used in the proposed study include: 1) *Standardized Trauma Interview*^[90], a 41-item clinician-administered interview that gathers information on relevant aspects of the trauma and demographic information at baseline; 2) *Difficulties in Emotion Regulation Scale*^[58], which measures ED and includes six subscales (non-acceptance of emotions, difficulty with goal-directed behavior in the presence of negative emotions, difficulty controlling impulses in the presence of negative emotions, lack of awareness of emotions, limited use of effective emotion regulation strategies, and lack of understanding of emotions); 3) *Five Facet Mindfulness Questionnaire*^[91] will assess mindfulness; it includes five facets (observing, describing, acting with awareness, non-judging of inner experience, and non-reactivity to inner experience); 4) Self Compassion Scale, Short Form^[92] will assess self compassion. 5) *The PTSD Checklist for DSM-5*^[93] will be used as another self-report measure of PTSD. 6) *The Beck Depression Inventory, II*^[94] will be used as another self-report measure of depression symptoms. Diagnoses at pre- and post-assessments also will be assessed by the *MINI International Neuropsychiatric Interview*^[95] (for MDD) and the *Clinician Administered PTSD Scale*^[96] (for PTSD), both of which are semi-structured interviews. 7) The *Positive and Negative Affect Scale*^[97] will be used to assess trait level positive and negative affect.

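### Virtual assignment tells the pre-assessor the subject's arm, and nothing keeps that person from the same subject's post-intervention CAPS and MINI, whose raters are meant to be blind

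*Combined protocol and SAP*

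**What the plan says.** All of this is in Study design and methods.

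- **Timing of randomisation (Procedure).** "Following the pre-intervention assessment, they will be randomly assigned using a random number generator".
- **Concealment (Procedure).** Opaque envelopes are used "so the study staff that are enrolling subjects do not know in advance which treatment condition will be assigned next". The person who generates the sequence is not blind, does not recruit and does not collect outcomes.
- **Virtual assignment (Procedure).** Two staff members who take no part in recruitment or assessment "will have the allocation sequence and will provide it to the staff member doing the pre-assessment following the completion of the interview".
- **Rater blinding (Procedure, the very next sentence).** The "staff members who will conduct the CAPS and MINI (to assess other Axis I disorders) will be blind to group assignment". No exception is made for virtual assignment.
- **When CAPS and MINI are given.** Psychological Measures says "Diagnoses at pre- and post-assessments also will be assessed by the" MINI and the CAPS. In the schedule table, the marks for the "Clinician Administered PTSD Scale" and the MINI appear to stand under Screen and Post, with none under Pre or follow-up.

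**The concern.** The design takes care to separate knowledge of the arm from assessment: the sequence generator collects no outcomes, and the virtual holders do no assessing. The virtual step then hands the arm to an assessor. If that person later conducts the same subject's post-intervention CAPS and MINI, the rating is made by someone who knows the arm, and the blinding rule fails for that subject.

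CAPS and MINI are the only measures for which the plan promises blind raters. A report that repeats the promise could be wrong for some subjects, and the protocol gives no way to tell how many. Pre-assessments may be held by phone or Zoom, so the path may be used often; the share is not stated.

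**Working it through.** The plan gives no figure on this point to reproduce, so the check is a comparison of the passages.

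1. **Who learns the arm, and when.** In virtual assignment it is the pre-assessor, once the pre-intervention interview is over.

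2. **Could that person be a CAPS or MINI rater at baseline?** By Psychological Measures, yes, since both interviews belong to the pre-assessment. By the schedule table they fall at Screen. Two details favour the text. The five eligibility instruments given through the parent study do not include CAPS or MINI. The pre and post visits are each put at about 3 hours, although the table's Pre column shows only the trauma interview and the emotion regulation scale. This does not settle the question.

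3. **Could that person rate the subject after the intervention?** Text and table both place CAPS and MINI at Post. Procedure, Study Design, Training and Setting do not say who does the post ratings, and none of them excludes the pre-assessor.

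4. **Combining 2 and 3.**
   - Interviews at Pre, same person rates at Post: the rating is informed and the rule fails for that subject.
   - Interviews at Pre, a rater who was not told rates at Post: the rule holds.
   - Interviews at Screen, pre-assessor rates at Post: the rule fails for that subject.
   - Interviews at Screen, a rater who was not told rates at Post: the rule holds.

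   The outcome depends only on who rates at Post, which is not stated. The mismatch between text and table does not remove the gap.

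5. **Baseline ratings.** Whether done at Screen or at Pre, they precede disclosure and are unaffected.

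6. **Concealment.** The subject's own assignment is released only after the interview. Later assignments would be exposed only if the whole sequence is handed over **and** the pre-assessor enrols later subjects. Grammatically the pronoun in the virtual step refers to the sequence. The second condition is nowhere stated: consent is taken by a co-investigator or research fellow, and overlap with the pre-assessor is not described.

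7. **Size.** Let v be the share assigned virtually, s the share of those whose post rater was told the arm, and d the average difference between arms that knowing the arm adds to an informed rater's scores. If v and s are the same in both arms, the average bias is v × s × d. With v and s each between 0 and 1, this lies between 0 and d. The documents give none of the three, so no single value can be defended.

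**The case against.** **The two sentences can be read together.** They are adjacent and describe staff differently: one names the person doing the pre-assessment, the other the people who conduct CAPS and MINI. A natural joint reading is that one person learns the arm while separate raters stay blind. This stands to the extent that there is no certain contradiction. It does not close the gap, because the separation is not written down and blinding that rests on unwritten staffing cannot be verified.

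A reader might also infer more than the documents support:

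- **That concealment is broken.** Both conditions in step 6 of the working are needed, and the second is not stated. Reading the pronoun as the whole sequence would also defeat the purpose of keeping it with two independent holders. The wording still needs tightening.
- **That staff who see past assignments can predict the next, and only on the virtual path.** In a block of 20 with m = 10 per arm (1:1 is assumed; the ratio is not stated), someone who knows every earlier assignment in the block guesses m + 2^(2m−1)/C(2m, m) − 1/2 = 10 + 524,288/184,756 − 0.5 = 12.34 of 20 correctly, or 61.7%. The same holds for envelopes if the same staff learn each result. The plan does not say who opens the envelopes, so the in-person path cannot be called safer. Stratification would also require tracking each stratum.
- **That the Aim 2 results or their type I error are compromised.** Aim 2a uses a self-report scale and Aim 2b device-recorded skin conductance. No between-arm test of CAPS or MINI is specified, so an inflated error rate would belong to no planned test. The trauma interview is outside the blinding rule, and skin conductance is skipped when laboratory attendance is unsafe, which is when virtual assignment is most likely.

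**Conclusion.** The point holds as an unreconciled pair of statements. A specified disclosure step puts the plan's only promised rater blinding at risk at the post-intervention visit. It is more than a missing detail, because the plan names an assessor as the recipient when it could have named someone else.

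Severity is low to moderate. The exposure is confined to subjects assigned virtually whose post CAPS or MINI is done by the person who was told the arm. The conclusion assumes only that nothing outside these documents, such as a staffing manual, already separates the two roles. If something does, a sentence in the protocol is enough.

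**What to change.** In Procedure, replace the virtual step with wording to this effect: one of the two independent staff members releases only the current subject's assignment, after the pre-assessment is complete, to the subject or to a scheduler who does not rate CAPS or MINI; the sequence itself is not shared; anyone who learns a subject's assignment does not conduct that subject's post-intervention CAPS or MINI. Bring the schedule table and Psychological Measures into agreement on when the baseline CAPS and MINI are given.

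The inclusion rationale refers to recruitment difficulties since the study began, so some subjects may already have been assigned by the present path. For them, use an existing rater who was not told the assignment where one is available, and report how many post-intervention CAPS and MINI ratings were made by an informed rater.

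The cost is one extra message per subject and a small scheduling constraint. The two independent staff already exist. Where no uninformed rater is available for a subject already assigned, the remedy is disclosure of the count, not a new hire.
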